### 3.0 Intervention to be studied

The web-based SMYLS app consists of three major components: patient-centered educational materials; symptom monitoring and tracking; and young adult (YA) and A/CG-provider communication. Educational materials on SCD pathophysiology, home management strategies, and symptom prevention are derived from patient-facing, guideline-based information endorsed by authoritative sources. Educational materials have been translated to an app-friendly format and are subdivided by age (up to 12 years, 12 – 17 years, adult), role (parent), or “hot” topics (hydroxyurea, research participation, hematopoietic stem cell transplantation). For symptom monitoring, pain is the predominant symptom YA and A/CG track via the app. YA and A/CG record pain scores and location via an avatar, then proceed through a series of screens to record

additional information pertaining to the pain, and additional symptoms that may co-occur. A graph is available by which YA and A/CG can observe trends in recorded pain, including specifics such as the numeric pain rating, the site of the pain, description of the pain, and actions taken to relieve pain. YA-provider or A/CG-provider communication is facilitated by a health history page intended for YA or A/CG to complete with their provider. In addition to this static option, the app also includes a link that takes the user to MyChart to complete a message to the provider via the EHR portal. Ideally, YA or A/CG will use the app daily to record and track symptoms, and as needed to access educational materials and message providers, and providers will communicate via messaging with YA or A/CG. However, a primary aim of this study is to assess participant engagement with the app. User activity and records are recorded in a secure database housed at TACHL for analysis.

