## 10.0 Study Design / Methods

This single-group study will assess feasibility to test reach, efficacy, adoption, implementation, and maintenance of SMYLS using the RE-AIM framework (25) (Table 1) with 30 adolescents (A)/caregivers (CG), 15 young adults, and 5 healthcare providers involved with their care. YA and A/CG will be enrolled for a total of 6 months (12-week intervention with 3-month follow-up). Providers will be enrolled for as long as an adolescent under their care is currently enrolled ( $\geq 6$  months). We will obtain outcomes data on feasibility, self-management behaviors, and healthcare activities (primary aim), and transition readiness, symptoms, quality of life, and healthcare utilization (secondary aim). Measures include patient report via surveys, data recorded via the app, such as symptoms and app use, communication content from MyChart messaging, and in-depth data via key informant interviews.

Table 1 outlines the data to be collected and survey instruments to be administered at each of four data collection points: baseline, 6-weeks (mid intervention), 12-weeks (end of intervention), and 3-months post-intervention. Participants will be given the option of completing surveys in one of three ways: in person in a private room at the MUSC Pediatric Sickle Cell Clinic, by phone, or electronically through a link to REDCap. Estimated time for completion of surveys at each of the 4 visits is approximately 45 minutes. For in-person and phone data collection methods, all data will be recorded in REDCap by the PI or IRB-approved study personnel. Reimbursement to young adult and adolescent/caregiver dyads will be \$50 in the form of a gift card presented at each of the 4 data collection points. For A/CG participants, payments will be given to the caregiver; in the case of phone or electronic data collection, participants will be mailed the gift card by certified mail or will receive an electronic gift card via email.

Healthcare providers will complete a demographic survey in person or electronically at baseline. Subsequently, no surveys will be administered to healthcare providers.

Healthcare providers' study activities involve communicating with the young adults and adolescents/caregivers via MyChart.

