Implementation: (primary aim) Technology (A/CG, HCP) Consistency of intervention (A/CG, HCP)	Reported problems; fidelity to protocol; assistance/instructions required	Quality checks Semi-structured interview	Weekly Post intervention
Maintenance: (primary aim) Projection of future adoption (A/CG, HCP)	Perceptions of intervention; perceptions of feasibility; interest in continuing intervention	Semi-structured interview	Post intervention

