## 11.0 Data Management

**Sex as a biological variable.** We recruit equal numbers of male and female adolescents and preliminarily explore for differences by sex in outcomes, such as acceptability, satisfaction, communication content, symptoms, quality of life, transition readiness, and utilization by conducting preliminary subgroup analyses in preparation for the subsequent larger trial.

**Feasibility processes.** Variables will include those pertaining to study procedures as well as participant variables. Specifically, 95% confidence intervals for proportions will be used to estimate dichotomous outcomes including the proportion of YA, A/CG who agree to participate out of the number approached, the proportion adherent to the intervention protocol, i.e., providing daily symptom monitoring/tracking, using the education component, responding to messaging, lost to follow up, etc. For the continuous feasibility measures (length of time spent in app components), frequency distributions and the median and mean responses with 95% confidence intervals will be obtained. Benchmarks for feasibility success are recruitment rate of at least 2 YA or A/CG per week, retention rates of 70%, use of at least one component of the app  $\geq 2$  days per week (adherence), and expressed satisfaction in key informant interviews (37).

**Outcome measures and estimates of variability.** Secondary aim outcomes variables will include measures of symptoms (pain, fatigue, depression, anxiety, sleep interference), quality of life, transition readiness, and utilization (number of appointments kept, number of ED visits). Demographic and clinical variables obtained at baseline will be described via measures of central tendency (mean, median), variability and frequency distributions as appropriate. Additionally, demographic and clinical characteristics for those who adhered to the study protocol versus those who did not adhere (non-adherers and drop outs) will be compared to better describe the study population. For continuous quality of life measures, the difference between pre-and post-intervention measurements will be estimated via 95% confidence intervals. To assess preliminary intervention effects, we will conduct repeated measures ANCOVA with variables in individual models adjusting for “dose” defined as number of times each portion of the app was accessed, total time spent in each portion of the app, number of days symptoms were recorded, and number of A/CG-provider messages.

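### Maintenance is labelled a primary-aim element but is measured only by interviews about future intentions; no observed behaviour from the 3-month follow-up is assigned to it

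*Combined protocol and SAP*

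**What the plan says.** Section 10.0 (Study Design / Methods) sets out to assess "feasibility to test reach, efficacy, adoption, implementation, and maintenance of SMYLS". In Table 1 of that section the Maintenance row reads "primary aim) Projection of future adoption (A/CG, HCP". Its measures are "Perceptions of intervention; perceptions of feasibility; interest in continuing intervention", its only source is the semi-structured interview, and its only time point is post intervention. The interview analysis in section 11.0 likewise describes its product as expected future use.

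On duration, section 10.0 states: "YA and A/CG will be enrolled for a total of 6 months (12-week intervention with 3-month follow-up". Data are collected at "baseline, 6-weeks (mid intervention), 12-weeks (end of intervention), and 3-months post-intervention".

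On behaviour, section 3.0 says of the app: "User activity and records are recorded in a secure database housed at TACHL for analysis". Table 1 lists application data capture as ongoing, but under Efficacy and Adoption. Section 10.0 has all patient–provider MyChart messages retrieved for analysis, pays $2 per message up to $20, and tallies that payment at week 12. The adherence benchmark in section 11.0 is "use of at least one component of the app" on two or more days a week. No period is attached to it, and no benchmark refers to the follow-up.

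**The concern.** An expressed wish to continue is not continued use. Here it is also collected from a favourable subset: people who finished 12 weeks, agreed to be interviewed and, among dyads, were purposefully chosen. Participants who dropped out contribute nothing. The study could report encouraging maintenance findings while use had ceased, and nothing assigned to the Maintenance row would show the difference.

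Section F of the safety monitoring plan says the information gained will inform a larger efficacy trial. Whether engagement persists once the intervention period ends is something that trial's designers will want to know, and the participants are already enrolled and in contact for those months.

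A related gap is that the documents do not say whether the app remains available after week 12. The 3-month survey could therefore describe outcomes after exposure has ended, or outcomes under continued exposure.

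**Working it through.** The plan gives no sample size, precision or target for maintenance, so there is no stated figure to reproduce. The check has three parts.

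**1. What is assigned to each element (Table 1)**

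| Element | Source | Observed behaviour? | Follow-up use specified? |
|---|---|---|---|
| Adoption | App data capture, interview, quality checks | Yes | No |
| Maintenance | Interview only | No | No |

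The integration matrix in section 11.0 combines app use with surveys, messages and interviews across RE-AIM as a whole. It does not define a use measure after week 12 or attach one to Maintenance.

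**2. Who can contribute to Maintenance**

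Inputs: 30 dyads and 15 young adults (section 6.0); interviews with up to 15 dyads and up to 15 young adults, all 12-week completers (section 10.0).

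- Patient units enrolled: 30 + 15 = 45.
- Most that can be interviewed: 15 + 15 = 30, and 30/45 = 67%. Among dyads, 15/30 = 50%.
- Units with no maintenance information at all: at least 15/45 = 33%.
- If retention to week 12 were exactly the 70% benchmark in both groups (an assumption; the benchmark gives no time point), 0.70 × 30 = 21 dyads and 0.70 × 15 = 10.5 young adults would remain. The ceiling would then be 15 + 10 = 25 of 45 (56%).
- Up to 5 provider interviews are additional.

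Enrolled time after the intervention is about 12 of 24 weeks, or 50%.

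**3. Precision of an observed measure**

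The documents give no expected proportion, so 30% to 70% is assumed. The Wilson 95% half-width is

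z/(1 + z²/n) × √[p(1−p)/n + z²/(4n²)], with z = 1.96.

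Worked case, n = 45 and x = 22 (p = 0.489): 1.96/1.0854 × √(0.005553 + 0.000474) = 0.140.

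| Units | Count | Proportion | Wilson 95% CI | Half-width |
|---|---|---|---|---|
| 45 (all enrolled) | 14 | 31% | 20–46% | 13.1 points |
| 45 | 22 | 49% | 35–63% | 14.0 points |
| 45 | 31 | 69% | 54–80% | 13.1 points |
| 31 (70% of 45 = 31.5) | 9 | 29% | 16–47% | 15.2 points |
| 31 | 16 | 52% | 35–68% | 16.6 points |
| 31 | 22 | 71% | 53–84% | 15.2 points |

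The simple normal approximation at 50% with 45 units gives 1.96 × √(0.25/45) = 14.6 points. The same intervals apply to the proportion of units sending any MyChart message. This is descriptive precision, in keeping with the 95% intervals section 11.0 already plans for feasibility proportions.

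**The case against.** The strongest objection is that the follow-up may hold no app use to observe. The schedule calls week 12 the end of the intervention and the last visit post-intervention, and message payments close at week 12. That wording leans towards access ending then, although no section says so. A reader might infer that three months of app logs are being ignored, or that the app ought to be kept open. The documents do not support either inference. Keeping it open would be a design change, and it would give up what may be an off-intervention assessment. This part of the objection stands, and it makes any app-based measure conditional. It does not reach MyChart messages, which can be sent without the app.

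The plan is also open about its construct: Table 1 calls it a projection, and Aim 1 in section 1.0 does not name maintenance. A reader might infer an internal contradiction, but there is none. The weakness is one of measurement, for an element that section 10.0 says is tested and Table 1 ranks as primary.

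Observed use in follow-up would not be unprompted either. Section C of the safety monitoring plan keeps weekly contact throughout enrolment, and a $50 payment falls at the 3-month point. That stands and should be disclosed, but supported use is still behaviour.

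Finally, a reader might infer that the follow-up adds nothing. That goes too far: the 3-month surveys of self-efficacy, transition readiness, symptoms and quality of life bear on whether effects last. Nor should maintenance be redefined purely as patient app use, because the row also covers providers.

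**Conclusion.** The concern holds as a weakness of measurement. A primary-aim element rests entirely on stated intention from at most 30 of 45 patient units (67%), all willing 12-week completers, plus up to 5 providers. No observed behaviour from roughly half of the enrolled time is assigned to it. The direction of the resulting bias is a judgement: selection of completers and volunteers probably favours stated interest, but the documents give no figures to size it.

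The conclusion on messages assumes that transcript retrieval can run to month 6; section 10.0 gives no end date for it. The conclusion on app use depends on an answer the documents do not give, namely whether access and logging continue after week 12. The precision figures assume true proportions between 30% and 70%. The change is worth making before analysis, but the gap does not invalidate the study.

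**What to change.** Keep the interviews with patients, caregivers and providers, and add observed follow-up behaviour to the Maintenance row of Table 1, with all 45 enrolled units as the denominator:

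1. **MyChart messages.** Report the number sent in weeks 13–24 and the proportion of units sending any, with a 95% CI. These messages fall after the payment tally and do not depend on app access. State that retrieval runs to month 6.
2. **App access.** State whether access and logging continue after week 12.
   - *If they do:* report the proportion of units meeting the existing benchmark (one or more components on two or more days a week) in weeks 13–24, with a 95% CI. Note that weekly contact and the 3-month payment make this supported use. Present the 3-month survey alongside each unit's use in that period.
   - *If they do not:* label the app element as intention to continue, and describe the 3-month survey as off-app.

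The app does not have to be kept open. The cost is revised wording in Table 1 and section 11.0 and a little more data extraction, with no added visits. The drawback is that maintenance may look less favourable than stated intention.

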### Minimizing Research-Associated Risk:

Diligent study safety monitoring will be conducted by the PI, Program Coordinator (PC), and the study's Safety Monitoring Committee (SMC) throughout the conduct of this study in compliance with the following required elements of MUSC IRB's continuing review process:

1. Tracking and follow-up of participant accrual (inc. withdrawn consents) will minimize risk by identifying, disclosing, and mitigating any potentially unknown risk(s) of harm to study participants. These risks are minimal.
2. Timely and appropriate reporting of informed consent process deficiencies, protocol deviations, privacy breaches, conflicts of interest, and/or changes in personnel.
3. Ongoing soliciting, monitoring and appropriate reporting of adverse event activities.
4. Timely and appropriate IRB submission of safety-related documents such as audit reports, sponsor progress reports, SMC reports, and other materials or communications that might impact the safe conduct of this study.
5. Active cooperation with the IRB, ACO, sponsor, and other applicable entities in the event of a random or for-cause internal or external audit.

## 11.0 Data Management

**Sex as a biological variable.** We recruit equal numbers of male and female adolescents and preliminarily explore for differences by sex in outcomes, such as acceptability, satisfaction, communication content, symptoms, quality of life, transition readiness, and utilization by conducting preliminary subgroup analyses in preparation for the subsequent larger trial.

**Feasibility processes.** Variables will include those pertaining to study procedures as well as participant variables. Specifically, 95% confidence intervals for proportions will be used to estimate dichotomous outcomes including the proportion of YA, A/CG who agree to participate out of the number approached, the proportion adherent to the intervention protocol, i.e., providing daily symptom monitoring/tracking, using the education component, responding to messaging, lost to follow up, etc. For the continuous feasibility measures (length of time spent in app components), frequency distributions and the median and mean responses with 95% confidence intervals will be obtained. Benchmarks for feasibility success are recruitment rate of at least 2 YA or A/CG per week, retention rates of 70%, use of at least one component of the app  $\geq 2$  days per week (adherence), and expressed satisfaction in key informant interviews (37).

**Outcome measures and estimates of variability.** Secondary aim outcomes variables will include measures of symptoms (pain, fatigue, depression, anxiety, sleep interference), quality of life, transition readiness, and utilization (number of appointments kept, number of ED visits). Demographic and clinical variables obtained at baseline will be described via measures of central tendency (mean, median), variability and frequency distributions as appropriate. Additionally, demographic and clinical characteristics for those who adhered to the study protocol versus those who did not adhere (non-adherers and drop outs) will be compared to better describe the study population. For continuous quality of life measures, the difference between pre-and post-intervention measurements will be estimated via 95% confidence intervals. To assess preliminary intervention effects, we will conduct repeated measures ANCOVA with variables in individual models adjusting for “dose” defined as number of times each portion of the app was accessed, total time spent in each portion of the app, number of days symptoms were recorded, and number of A/CG-provider messages.

**Content of patient-provider communication.** Our methods of analysis are modeled after the work of Goldsmith and colleagues, who created a framework of caregiver communication types from qualitative data, and subsequently used the framework as a coding structure (38, 39). We will analyze the messages between YA and providers and A/CG and providers using directed content analysis (40) and nVivo 11 (41). We will build on the work of Goldsmith (39) and of Jacob et al. (42), who applied an inductive approach to analyze text messages and developed a framework of healthcare activities that occur via text communications. According to Jacob’s framework, the two main healthcare categories are collaborating and coaching, and the four subcategories are screening, referring, informing and supporting. Jacob’s framework will serve as the initial coding framework for our analysis. Data that do not fit in any of the framework codes will be analyzed separately to identify new, additional codes. We will then conduct frequency

counts to identify the number of YA and A/CG with each type of code and the number and types of codes for each YA and A/CG. Also modeled after the work of Goldsmith and colleagues (38), we will conduct preliminary analyses to explore relationships between number and types of healthcare activities and self-management and symptom outcomes in A/CG.

**Key informant interview analyses.** Data will be analyzed using content analysis (43) and nVivo 11 (41). Analysis will be conducted in three phases. First, during preparation, the unit of analysis will be selected based on meaning, and may include a word, sentence, phrase, or paragraph. We will also immerse ourselves in the data to make sense of the whole by listening to audio recordings and reading transcripts multiple times. Second, we will organize the data using a deductive approach and the RE-AIM framework as an unconstrained coding matrix. To use an unconstrained matrix, we will apply the principles of inductive analysis to identify categories within the RE-AIM framework (43). Data will be reviewed and coded within the identified categories. Third, results will be described through the meaning of categories and subcategories. Emergent categories and subcategories will provide essential information on overall perceptions of the intervention, satisfaction, acceptability, and anticipated future use.

**Integration of adolescent, caregiver, and provider findings.** A matrix using the RE-AIM framework will be developed to assimilate results obtained from analysis of app use, surveys, YA-provider and A/CG-provider messages, and key informant interviews and determine convergence and divergence of findings. In addition to determining implementation feasibility, integration of findings will lead to development of a model of healthcare activities occurring via YA – provider and A/CG – provider communication associated with the development of self-management behaviors.

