## **7.0 Setting**

We will recruit 30 adolescents ages 11 – 17 and the parent/primary caregiver to participate as an A/CG dyad (n = 60) and 15 young adults ages 18 – 25 (total n = 75) from the MUSC Pediatric Sickle Cell Clinic, which serves over 500 children with SCD, approximately 150 of whom are adolescents ages 11 – 17 years. The Pediatric Sickle Cell Clinic continues to care for young adults with SCD up to 25 years of age prior to transitioning to an adult provider. Healthcare providers will also be recruited from the MUSC Pediatric Sickle Cell Clinic. However, as the purpose of the study is to test the feasibility of an intervention for improving self-management, young adult and adolescent/caregiver participants will use the interventions in their homes or in the settings of their everyday life.

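### Does the app-use (adherence) benchmark need a required share of participants and a week rule before feasibility can be judged?

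*Combined protocol and SAP*

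**What the plan says.** All the relevant text is in the combined protocol and SAP, mostly in section 11.0 Data Management.

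- **Benchmarks** (feasibility processes paragraph). Recruitment and retention have study-level thresholds: "recruitment rate of at least 2 YA or A/CG per week" and, for retention, 70%. The app-use item reads "retention rates of 70%, use of at least one component of the app", at 2 or more "days per week (adherence), and expressed satisfaction in key informant interviews".
- **Estimated proportion** (same paragraph). Dichotomous outcomes get 95% confidence intervals, among them "the proportion adherent to the intervention protocol, i.e., providing daily symptom monitoring/tracking, using the education component, responding to messaging, lost to follow up, etc".
- **Descriptive comparison** (outcome measures paragraph). Baseline characteristics are compared between "those who adhered to the study protocol versus those who did not adhere (non-adherers and drop outs"), in order to describe the study population better.
- **Status.** Section 3.0 says that "a primary aim of this study is to assess participant engagement with the app". Table 1 places adherence under Adoption, marked as a primary aim.
- **Unit and window.** Section 7.0 recruits 30 adolescents, each with a caregiver, "to participate as an A/CG dyad (n = 60) and 15 young adults". Section 10.0 sets a "12-week intervention with 3-month follow-up".

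The supplied text gives no share of participants, no number of qualifying weeks and no rule on whose use counts within a dyad.

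**The concern.** Of the benchmarks listed, only this one sets a level of app use, and app use is what the intervention consists of. Read as a rule for each participant, it has no pass point. Read as a group average, it has one, but heavy users could carry the average while many participants fall short. The plan does not choose between these readings.

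The word also appears in three settings that are not expressly linked: the benchmark (any component, 2 or more days a week), the estimated proportion (described through daily tracking, education use, message response and so on), and the adherer comparison (no cut-off). Daily tracking is far more demanding than use on 2 days a week, so the second could be read as contradicting the first.

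At stake is the success verdict on one benchmark of primary Aim 1, and who falls into the non-adherer group. If the rule were picked after the app logs had been seen, the same logs could be called success or failure.

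**Working it through.** The documents give no expected app use, sample-size calculation or interval width, so there is no stated figure to reproduce. The check asks how far the unstated rules could move the answer. All levels of use below are assumptions.

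**Inputs from the plan.** 30 dyads + 15 young adults = 45 units (sections 6.0 and 7.0); 12 weeks of intervention (section 10.0); 2 or more days a week and 70% retention (section 11.0).

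**Step 1: equal use in every unit.** Let p be the chance of using the app on a given day, with days independent. The chance that a week qualifies is w = P(Bin(7, p) ≥ 2). The share adherent is then w^12 if all weeks must qualify, P(Bin(12, w) ≥ 9) if 9 of 12 must, and P(Bin(84, p) ≥ 24) if the 12-week average must be at least 2 days (24 of 84 days).

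| p (days/week) | w | all 12 weeks | 9 of 12 | 12-week average |
|---|---|---|---|---|
| 0.3 (2.1) | 0.6706 | 0.8% | 40.4% | 65.2% |
| 0.4 (2.8) | 0.8414 | 12.6% | 89.1% | 98.9% |
| 0.5 (3.5) | 0.9375 | 46.1% | 99.5% | about 100% |
| 0.7 (4.9) | 0.9962 | 95.5% | about 100% | about 100% |

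**Step 2: use varying between units.** Let p follow a beta distribution with SD 0.20 and average the same three quantities over it.

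| mean p (days/week) | all 12 weeks | 9 of 12 | 12-week average |
|---|---|---|---|
| 0.3 (2.1) | 17.8% | 41.9% | 47.6% |
| 0.4 (2.8) | 30.5% | 61.8% | 68.1% |
| 0.5 (3.5) | 47.5% | 78.7% | 83.7% |

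Most of the spread comes from the all-weeks rule. Between 9 of 12 weeks and the 12-week average, the gap in this table is 5 to 6 percentage points.

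**Step 3: group average, varied use at 2.8 days.** With no dropout, the SD of a unit's weekly average is sqrt((7 × 0.2)² + 0.2 × 84/144) = 1.44 days. The standard error over 45 units is 1.44/√45 = 0.215, and (2.8 − 2)/0.215 = 3.7, so the rule is met almost surely. That depends on complete data. Retention at its benchmark is 0.70 × 45 = 31.5, so 32 units. If the other 13 contribute no use but stay in the denominator, the mean is 2.8 × 32/45 = 1.99 days, and in simulation the rule is met about 48% of the time. If they leave after week 3 it is met about 85% of the time, and after week 6 about 98%.

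**Step 4: what a required share would mean.** Suppose retention is exactly 32 of 45 and all losses fall before week 12, with lost units counted as non-adherent. Then 70% of enrolled units means 32 of 32 retained units must adhere. If 70% of retained units is required, 0.70 × 32 = 22.4, so 23 units, which is 23/45 = 51.1% of enrolled. Nothing in the plan favours one over the other.

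**Step 5: what is reported whatever the rule.** Section 11.0 gives frequency distributions, medians and means with 95% intervals for time in app components. It enters times accessed, total time and days with symptoms recorded as continuous dose in the outcome models. Section 3.0 says user activity is stored for analysis. None of this needs an adherence cut-off.

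**The case for a change.** The strongest case for a change is that the plan itself sets benchmarks for success, so each should be decidable. Recruitment and retention are; this one is not, unless a group average is meant, and the plan does not say so. The estimated proportion points towards a participant-level rule. Writing the rule down would take a paragraph and no new data, and would remove any doubt about choices made after the logs were seen. Section F says that what is learned on uptake and adherence will inform a larger trial.

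The factual part of this stands: the share, the week rule and the treatment of dyads are not written, and the three uses of the word are not expressly tied together. Three things limit what follows.

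- Adherence is not left without meaning. The benchmark attaches the label to a stated criterion, and the natural reading carries it to the other two uses in the same section. The list containing daily tracking mixes in loss to follow-up and ends open, so it reads as a loose set of separate outcomes, not a rival definition.
- The result that a group average is met almost surely holds only without dropout, as step 3 shows. It is weak evidence that the benchmark would pass too easily.
- Any particular week rule or share would be a preference brought in from outside the plan. The text supports no single choice, and a share written in now would give a sharper verdict without better information about engagement.

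**Conclusion.** This is a gap in detail that analysts can fill sensibly, and no change to the plan is called for. The criterion is given (any component, 2 or more days a week), and the window and unit can be inferred (12 weeks; one young adult or one dyad, 45 in all). An analyst would report the proportion meeting the criterion with its 95% interval, state the week rule and how dropouts and dyads were counted, and show the distribution of use beside it.

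The possible size is real when use is low: under the assumed varied use at 2.8 days a week, 30.5% to 68.1% of units count as adherent. With equal use on 70% of days the range is 95.5% to about 100%. Both rest on assumed use and independent days, with no dropout.

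The consequence stays small because the supplied text ties no go/no-go decision to this benchmark, the adherer comparison is descriptive, and feasibility is also judged through interviews and the RE-AIM matrix in section 11.0. An unsettled pass point would leave one verdict open to interpretation. It would not bias the app-use estimates or hide them from the reader.
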